## 9. Study Assessments

## 9.1. Efficacy Assessments

Tumour response will be determined locally according to Recommendations for Initial Evaluation, Staging and Response Assessment of Hodgkin and non-Hodgkin Lymphoma [36]. Investigator assessment will be applied as a measure for assessment of tumour response and as a basis for all protocol guidelines for management of the patient related to disease status. CT or MRI scans are the required methods for tumour assessments. The same method of assessment and the same technique should be used to characterize each lesion at baseline and during follow-up.

All scans and other data supporting efficacy measurements will be stored at the study site and available for subsequent collection, if necessary, for review by the Sponsor and/or independent external reviewer(s).

#### 9.1.1. Contrast enhanced CT examination or MRI

A baseline contrast-enhanced CT scan or MRI must be performed within 4 weeks prior to the first RTX infusion. Table 1-1 and Table 1-2 show the frequency of subsequent contrast enhanced CT scans/MRI per patient for follow-up.

A CT volume scan re-constructed in 3 mm slides with use of i.v.-injected contrast agent will be performed per examination. The target lesions will be selected and measured at baseline and followed at each efficacy assessment. The longest perpendicular diameters (major and minor axis) will be recorded in the eCRF.

#### 9.1.2. PET/CT and CT/MRI examination

PET/CT and CT or MRI imaging will be done at baseline and then at 3 and 6 months. CT with contrast or MRI will be performed at 12, 18, 24 months or until disease progression or other withdrawal for any other reason (whichever comes first). Baseline imaging must be performed within 4 weeks prior to administration of the first RTX infusion.

Standard institutional guidelines will be followed. The patient needs to be fasting during 6 hours prior to PET/CT imaging, water is allowed. The blood glucose level must be <11 mmol/L before injection of Fluor doxy glucose (FDG). Anti-diabetic drugs cannot be taken on the day of PET/CT examination.

PET/CT examination will be performed by a commercial combined PET/CT scanner. All scans should be performed on the same camera. PET/CT imaging will be performed about 60 to 70 minutes after i.v. administration of 5 to 10 mCi (185 to 370 MBq) of FDG. Same activity  $\pm 20\%$  and time window must be used in the subsequent PET scans.

PET/CT scans will be done before contrast enhanced CT or MRI when both modalities are to be done on the same day.

All measurements of uptake will be based on standardised uptake values (SUV). Lesions <15 mm in short axis with abnormal activity: focal, above the surrounding background, above average liver SUV.

Study Number: LYMRIT-37-07 Version 4.0 04 Oct 2021

#### **Guidelines for baseline CT/MRI examination:**

- 1) Target lesions on the CT/MRI scans do not need to match those evaluated on the PET scan.
- 2) Target nodes should be chosen according to Cheson criteria, version 2014 [35]
- 3) Up to 6 target nodes should be selected; there must be at least one target node
- 4) The largest target nodes should be selected
- 5) Nodes should be from different body regions if possible
- 6) Mediastinal and retroperitoneal nodes should be included as target nodes if involved
- 7) A measurable node must have a LDi greater than 1.5 cm
- 8) A measurable extranodal lesion should have an LDi greater than 1.0 cm

#### **Guidelines for baseline PET examination:**

- 1) Target lesions on the CT/MRI scans do not need to match those evaluated on the PET scan
- 2) The lesions with the highest activity level should be chosen for the PET scan

#### **9.1.3. PET/CT score**

PET is scored on a 5-point scale (5PS), and follow-up will be assessed as described below. In addition,  $SUV_{max}$  will be recorded, and lean body mass ( $SUL_{max}$ ) is optional. In case of discrepancy between the criteria below and  $SUV_{max}/SUL_{max}$  the Investigators will be involved in decision-making.

#### 5-point scale (5PS)

#### Negative

- 1 no uptake
- 2 uptake ≤ mediastinum\*
- 3 uptake > mediastinum but  $\leq$  liver\*

NOTE if mediastinal blood pool activity is equal or greater than liver then the uptake within the lesion should be compared with liver (lesion uptake less than liver=score 2; lesion uptake equal to liver = score 3)

#### **Positive**

- 4 moderately increased uptake compared to liver at any site
- 5 markedly increased uptake compared to liver at any site
- X new areas of uptake unlikely to be related to lymphoma

Mediastinal and liver uptake is defined as SUVmax ±10%

Consider binary response scale for lung, bone/bone marrow, liver and spleen involvement.

Images will be evaluated and scored according to the 5PS. The PET/CT scans will be scored with reference to sites of presumed lymphomatous involvement on the PET/CT staging scan (Deauville criteria).

## 9.1.4. Definitions of Tumour Response Criteria

Investigator assessment will be applied as a measure for assessment of tumour response and as a basis for all protocol guidelines for management of the patient related to disease status using Cheson criteria version 2014 [35] (see Table 9-1).

 Table 9-1
 Criteria for tumour response evaluation

Response and Site	PET/CT-Based Response	CT/MRI-Based Response
Complete	Complete metabolic response	Complete radiologic response (all of the following)
Lymph nodes and extralymphatic sites	Score 1, 2 or 3 with or without a residual mass on 5PS (Sec 9.1.3). It is recognised that in Waldeyer's ring or extranodal sites with high physiologic uptake or with activation within spleen or marrow (e.g. with chemotherapy or myeloid colonystimulating factors), uptake may be greater than normal mediastinum and/or liver. In this circumstance, complete metabolic response may be inferred if uptake at sites of initial involvement is no greater than surrounding normal tissue even if the tissue has high physiologic uptake.	
 
Target nodes/nodal masses must regress to ≤1.5 cm in LDi
 
No extralymphatic sites of disease
 

Non-measured lesion	Not applicable	Absent
Organ enlargement	Not applicable	Regress to normal
New lesions	None	None
Bone marrow	No evidence of FDG-avid disease in marrow	Normal by morphology; if indeterminate, IHC negative
Partial	Partial metabolic response	Partial remission (all of the following)
Lymph nodes and extralymphatic sites	Score 4 or 5 on 5PS (Sec 9.1.3) with reduced uptake compared with baseline and residual mass(es) of any size.	- ≥50% decrease in SPD of up to 6 measurable nodes target and extranodal sites
	At interim, these findings suggest responding disease	- When a lesion is too small to measure on CT, assign 5 x 5 mm as the
	At end-of-treatment, these findings indicate residual disease	default value  - When no longer visible, 0 x 0 mm  - For a node >5 x 5 mm, but smaller than normal, use actual measurement for calculation
Non-measured lesion	Not applicable	Absent/normal, regressed, but no increase
Organ enlargement	Not applicable	Spleen must have regressed by >50% in length beyond normal
New lesions	None	None

Response and Site	PET/CT-Based Response	CT/MRI-Based Response
Bone marrow	Residual uptake higher than uptake in normal marrow but reduced compared with baseline (diffuse uptake compatible with reactive changes from chemotherapy allowed). If there are persistent focal changes in the marrow in the context of a nodal response, consideration should be given to further evaluation with magnetic resonance imaging (MRI) or biopsy or an interval scan.	Not applicable
No response or stable disease	No metabolic response	Stable disease
Target nodes/nodal masses, extranodal lesions	Score 4 or 5 on 5PS (Sec 9.1.3) with no significant change in FDG uptake from baseline at interim or end-of-treatment	<50% decrease from baseline in SPD of up to 6 dominant, measurable nodes and extranodal sites; no criteria for progressive disease are met
Non-measured lesions Organ enlargement	Not applicable  Not applicable	No increase consistent with progression No increase consistent with
New lesions	None	progression None
Bone marrow	No change from baseline	Not applicable
Progressive disease  Individual target nodes/nodal masses Extranodal lesions	Progressive metabolic disease  Score 4 or 5 on 5PS (Sec 9.1.3) with an increase in intensity of uptake from baseline and/or New FDG-avid foci consistent with lymphoma	Progressive disease requires at least 1 of the following individual product of the perpendicular diameters (PPD) progression:  An individual node/lesion
	at interim or end-of-treatment assessment	must be abnormal with:  - LDi >1.5 cm and  - Increase by ≥50% from PPD nadir and  - An increase in LDi or SDi from nadir  - 0.5 cm for lesions ≤2 cm  - 1.0 cm for lesions >2 cm  In the setting of splenomegaly, the splenic length must increase by >50% of the extent of its prior increase beyond baseline (e.g. a 15-cm spleen, must increase to >16 cm). If no prior splenomegaly, must increase by at least 2 cm from baseline. New or recurrent splenomegaly
Non-measured lesions	None	New or clear progression of pre-existing non-measured lesions

Response and Site	PET/CT-Based Response	CT/MRI-Based Response
New lesions	New FDG-avid foci consistent with lymphoma rather than another aetiology (e.g. infection, inflammation). If uncertain regarding aetiology of new lesions, biopsy or interval scan may be considered	Regrowth of previously resolved lesions A new node >1.5 cm in any axis A new extranodal site >1.0 cm in any axis, if <1.0 cm in any axis, its presence must be unequivocal and must be attributable to lymphoma. Assessable disease of any size unequivocally attributable to lymphoma
Bone marrow	New or recurrent FDG-avid foci	New or recurrent involvement

### 9.2. Safety Assessments

Safety assessments will consist of monitoring and recording of AEs, including SAEs, the monitoring of haematology, blood chemistry, immunogenicity, vital signs, ECGs, physical condition and body weight as detailed in Section 1.2.

#### 9.2.1. Definition

#### 9.2.1.1. Definition of adverse event

An AE is defined as the appearance of (or worsening of any pre-existing) undesirable sign(s), symptom(s) or medical condition(s) that occur after the patient signed ICF has been obtained.

An AE can be any unfavourable and unintended sign (including an abnormal laboratory finding), symptom, or disease temporally associated with the use of a study drug, whether or not considered related to the study drug.

Abnormal laboratory values or test results occurring after informed consent constitute AEs only if they induce clinical signs or symptoms, are considered clinically significant, require therapy (e.g. blood or platelet transfusion) or require changes in medications. Laboratory abnormalities that meet the criteria for AE should be followed until they have returned to normal. Laboratory abnormalities not requiring clinical intervention or further investigation will be captured as part of overall laboratory monitoring and should not be reported as AEs.

AEs that begin or worsen after informed consent should be recorded in the eCRF. Conditions that were already present at the time of informed consent should be recorded in the patient's Medical History CRF page. All AEs should be reported until 4 weeks following their last RTX maintenance dose or 12 weeks after Betalutin administration for patients who do not qualify for RTX maintenance therapy (see Section 4.1). Only ADR (see Section 9.2.1.2) and AESI (see Section 9.2.1.7) will be reported during follow-up.

Please see Section 9.2.4 for guidance on AE reporting.

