### 4. Study Design

## 4.1. Overall Design

This protocol describes a Phase 1b open-label, single-arm, dose escalation study to investigate the activity and safety and preliminary efficacy of Betalutin combined with RTX in patients with FL who have received one or more prior therapies. It is planned that 6-12 evaluable patients will be enrolled in the study.

All patients will receive a single i.v. dose of RTX (375 mg/m^2) on Day -14, and then sequential i.v. administrations of lilotomab (40 mg) followed by Betalutin (10 or 15 MBq/kg) within 4 hours on Day 0. Patients will then be administered RTX (375 mg/m^2) i.v. on Days 7, 14, 21 and 28.

Patients will undergo clinical and laboratory assessments during screening/baseline and periodically during treatment as outlined in the Schedule of activities (Section 1.2). Two cohorts of 3-6 patients will be initially evaluated for DLT, in a 3+3 escalation pattern, before determining the subsequent Betalutin dose for the remainder of the study (Section 6.1).

Tumour-tissue biopsies and blood samples will be collected to study the mechanisms of tumour response to therapy as described in the biomarkers section (Section 9.4). The collection of these samples is optional and, at Radium Hospital (Oslo, Norway) only.

[figure not shown]
PET/CT and CT imaging (or MRI) will be performed at baseline and then at 3 and 6 months. CT with contrast (or MRI) will be performed at 12, 18, 24 months or until disease progression or withdrawal from the study for any other reason (whichever comes first).

Patients who achieve SD, CR or PR on their Month 3 imaging scan will be administered maintenance RTX 375 mg/m^2 i.v. or 1400 mg s.c. every 3 months for up to 2 years (8 infusions in total), or until disease progression or withdrawal from the study for any other reason (whichever comes first).

The schedule plan for dosing and imaging is illustrated in Figure 4-1.

Study Number: LYMRIT-37-07 Version 4.0 04 Oct 2021

Figure 4-1 Study dosing and imaging plan

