**Haematological:** Anemia, neutropenia or thrombocytopenia CTCAE (v4.03) grade 4 lasting >7 days, or grade 3 thrombocytopenia with clinically significant bleeding, or febrile neutropenia (ANC <1000/mm^3 with a temperature >38.3°C).

**Non-haematological**: An AE of CTCAE (v4.03) grade 3 or higher where the relationship to study treatment cannot be ruled out, and is not primarily related to disease, disease progression, intercurrent illness or concomitant medications that occurs within the first 12 weeks of treatment. Other clinically significant toxicities may also be considered to be DLTs by the Investigators and Sponsors, even if not CTCAE grade 3 or higher.

Responding patients (i.e. those having a CR, PR or SD response following Betalutin and the 4-weekly doses of i.v. RTX) will receive maintenance RTX every 3 months for up to 2 years (a total of 8 doses), or until disease progression, commencing at Week 14. This may be administered by either i.v. (375 mg/m²) or s.c. (fixed dose of 1400 mg) routes.

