## 8.2.11. Visits 16 (Month 3/Week 14) – Hospital Visit

Providing patient is deemed not to have PD following the Week 12 imaging scan (above), Rituximab maintenance dosing will commence, as outlined in Table 8-14.

Table 8-14 Procedures and assessments at Visit 16 (Week 14 [±7 days])

Assessment or Procedure	Explanation
Concomitant medication/therapy	Concomitant medication used since prior visit will be recorded
Physical examination	Any abnormal findings will be recorded in the AE record
Vital signs	Systolic/diastolic blood pressure, heart rate and body temperature
Rituximab administration	Weight, body surface area, dose administered, start and end time
$375 \text{ mg/m}^2 \text{ iv or } 1400 \text{ mg s.c.}$	of administration and pre-medication will be recorded
Adverse events	Any AEs occurring since prior visit will be recorded

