## **8.2.18.** Visit 23 (Month 24/Week 104) – Hospital Visit

Rituximab maintenance dosing and imaging, as outlined in Table 8-21.

Table 8-21 Procedures and assessments at Visit 23 (Month 24/Week 104 [±7 days])

Assessment or Procedure	Explanation	
Concomitant medication	Recording of concomitant medication used since the previous visit	
Physical examination	Any abnormal findings will be recorded in the AE record	
Vital signs	Systolic/diastolic blood pressure, heart rate and body temperature	
ECOG	ECOG performance status	
Haematology	Including haemoglobin, platelet count, white blood cell count and	
	differential (absolute count of neutrophils, lymphocytes,	
	monocytes, eosinophils and basophils)	
Serum biochemistry	Including sodium, potassium, calcium, magnesium, creatinine,	
	urea, uric acid, ALP, ASAT, ALAT, LDH, GGT, glucose, total	
	bilirubin and albumin	
Immunogenicity	Monitoring ADA response (lilotomab, Betalutin, RTX)	
Minimal Residual Disease 	MRD monitoring to assess early treatment response and detect	
(peripheral blood sample)	relapse	
Bone marrow biopsy	BM biopsy required for initial confirmation of CR if patient had	
	BM infiltration at baseline	
Radiology - CT scans with	CT or MRI of neck, thorax, abdomen and pelvis. Information	
contrast or MRI	about contrast medium, target lesion location and measurements	
	and non-measurable lesions will be recorded. The same camera	
	should preferably be used throughout the study	
Rituximab administration	Weight, body surface area, dose administered, start and end time	
$375 \text{ mg/m}^2 \text{ i.v. or } 1400 \text{ mg s.c.}$	of administration and pre-medication will be recorded	

Assessment or Procedure	Explanation
Adverse events	Any AEs occurring since prior visit will be recorded

Mandatory, unless relapse or disease progression has been clinically observed

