#### **9.2.4.** Reporting of adverse events

Any AEs that occur after a patient has signed the ICF and up to 12 weeks after their Betalutin or 4 weeks following their last maintenance RTX drug administration, must be reported, whether or not it is considered related to any of the study drugs. All AEs will be reported in the patient eCRFs. If more than one AE occurs, each event should be recorded separately. AEs and/or laboratory abnormalities shall be reported to the Sponsor according to the reporting requirements and within the time periods specified in the protocol. All AEs will be followed up until resolved or as clinically required. AEs that occur from 12 weeks after their Betalutin administration or 4 weeks after their last maintenance RTX drug administration, that are judged to be related to any of the study drugs will be reported when they come to the Investigator's attention.

Specific information about secondary malignancies such as leukaemia, MDS and aplastic anaemia or any other malignancy, will be collected up to 2 years after Betalutin administration or relapse of disease, including information about treatment given to the patient due to NHL (See Section 9.2.1.7).

Death is not defined as an AE but as an outcome of an AE. It is important that the event leading to the death be reported. It will be reported as an AE up to 12 weeks after their last study drug administration. Thereafter, death it will be collected in the eCRFs as survival information. It will be reported as the outcome of an ADR when it is judged as related to study drug.

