#### 10. Statistical Considerations

## **10.1.** Statistical Analyses

The study is a single-arm, open-label study to further assess the risk/benefit of a pre-dose of lilotomab and Betalutin to enhance tumour response to RTX therapy. Six to 12 patients is a reasonable sample size to evaluate any potential safety/tolerability signals and for obtaining preliminary estimates of the response rates and variability of the response rates.

The primary endpoint is the frequency and type of AEs. Study data will be summarised with respect to demographic and baseline characteristics, safety observations and measurements, efficacy observations and measurements (response rates, duration of response, PFS, TTP, OS), and PK measurements. Categorical data will be presented in tables; descriptive statistics will be used to summarise response rates, etc. Patients who have withdrawn from the study, including those who have died, will be counted as having PD for all visits after the time of withdrawal.

The number and percentage of patients with each response, and overall (CR + PR) will be presented for each time point for the ITT population. All data obtained after treatment with lilotomab/Betalutin will be summarized by the dose of Betalutin received and overall doses.

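### All-cause AE collection lasts 12 weeks or up to 108 weeks depending on the Month 3 scan, but Section 10.1 tabulates AEs by dose with no common window or patient-time

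*Combined protocol and SAP*

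**What the plan says.** Section 9.2.1.1 of the protocol sets the all-cause reporting period: "All AEs should be reported until 4 weeks following their last RTX maintenance dose or 12 weeks after Betalutin administration". The sentence goes on to limit the second period: "12 weeks after Betalutin administration for patients who do not qualify for RTX maintenance therapy". Section 9.2.4 repeats the two limits without that qualifier ("up to 12 weeks after their Betalutin or 4 weeks following their last maintenance RTX drug administration, must be reported"), and Section 9.2.5.1 does the same for SAEs.

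The Month 3 scan decides who qualifies. Section 4.1: "Patients who achieve SD, CR or PR on their Month 3 imaging scan will be administered maintenance RTX". Section 6.1 calls the same group responders: "Responding patients (i.e. those having a CR, PR or SD response following Betalutin". Section 8.2.11 puts it the other way round: "Providing patient is deemed not to have PD following the Week 12 imaging scan (above), Rituximab maintenance dosing will commence". The last scheduled maintenance dose is at "Visit 23 (Month 24/Week 104) – Hospital Visit", and Section 8.2.19 places the end of study visit 28 days later, at Month 25/Week 108.

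Table 3-1 defines the primary endpoint as the frequency and severity of AEs and SAEs and graded laboratory changes. It gives the same endpoint for the secondary objective of recommending a phase 2 dose. Section 10.1 specifies the grouping: "All data obtained after treatment with lilotomab/Betalutin will be summarized by the dose of Betalutin received and overall doses". Section 10.1.1 puts everyone who received any study drug into one safety population. The text mentions no fixed window, patient-time denominator or split between the early and maintenance periods. Section 10.1.2 refers only PK and biomarker analyses to the SAP; the Synopsis adds biodistribution.

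**The concern.** The length of AE collection depends on an outcome of treatment. A dose that controls the lymphoma better sends more patients into maintenance. Those patients are observed for longer and receive up to eight further rituximab doses. Even if two doses carried the same risk, the dose with more patients in maintenance would tend to show more patients with at least one AE. It would also tend to show worse worst-grade laboratory values, because more samples are taken after Week 12.

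The by-dose comparison within the primary safety summary is at stake, and through it the recommended dose. Rule 9 of Section 6.1 leaves the final recommendation to a review of all safety information at hand, not to DLT counts alone. With 3 to 6 patients per dose, the follow-up of one or two patients can shape the whole table.

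**Working it through.** **Windows, from the protocol's schedule.** Maintenance visits fall at Weeks 14, 26, 39, 52, 65, 78, 91 and 104, which gives the stated 8 doses. Last dose plus 4 weeks: 104 + 4 = 108 weeks, or 24.8 months. This reproduces Month 25/Week 108.

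- Not qualifying for maintenance: 12 weeks after Betalutin (2.8 months).
- Completing maintenance: 108 weeks. Ratio 108/12 = 9.0. Counted from the first rituximab on Day -14, it is 110/14 = 7.9.
- Stopping maintenance early: last dose plus 4 weeks, so Week 18, 30 or 56 after a last dose at Week 14, 26 or 52.

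**Effect on incidence.** The documents give no background AE rate, so the rate λ is an assumption: constant, and the same at both doses. P(at least one event in t weeks) = 1 − exp(−λt/52).

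| λ per patient-year | 12 weeks | 108 weeks |
|---|---|---|
| 0.2 | 4.5% | 34% |
| 0.4 | 8.8% | 56% |
| 0.8 | 17% | 81% |

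**Cohort averages at λ = 0.4.** Suppose k of 3 patients complete maintenance and the others stop at 12 weeks. Expected incidence = [k × 0.564 + (3 − k) × 0.088]/3.

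- k = 1: 25%
- k = 2: 41%
- k = 3: 56%

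The underlying risk is identical in all three. Restricted to 12 weeks, each gives 8.8%.

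**Patient-time.** With k = 1 the cohort contributes 108 + 2 × 12 = 132 weeks = 2.54 patient-years, and about 0.4 × 2.54 = 1.0 event if events recur at that rate. With k = 3 it contributes 324 weeks = 6.23 patient-years, and about 2.5 events. Events per patient-year are 0.4 in both.

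**Where the illustration does not apply.** Section 2.2.2.1 reports grade 3/4 neutropenia and thrombocytopenia in 20/36 (56%) each at 15 MBq/kg with the 40 mg lilotomab pre-dose. Section 7.2 puts the nadir at 5 to 7 weeks, and Section 2.4 has these toxicities resolving by 3 months in most patients. For such events the 12-week and 108-week incidences should be close. The constant-rate model describes background and late events only.

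**How likely a wide contrast is.** SD also qualifies for maintenance, so most patients may enter it. If 75% to 90% qualify (an assumption), the chance that at most 1 of 3 does is (1 − q)³ + 3q(1 − q)² = 15.6% at q = 0.75 and 2.8% at q = 0.90.

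**The case against.** The strongest defence has four parts.

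- **Escalation is protected.** Rules 1 to 8 of Section 6.1 turn on DLT counts, and the non-haematological DLT definition covers the first 12 weeks for everyone. A reader might infer that the plan biases escalation against the more effective dose. The documents do not support that. What remains is the by-dose AE table and the final recommendation under rule 9.
- **Collection does not simply stop.** A reader might infer that every patient who progresses is cut off at 12 weeks. The limit applies only to those who do not qualify for maintenance; later progressors are covered to 4 weeks after their last dose. Related AEs, related SAEs and AESIs stay reportable afterwards (Sections 9.2.4 and 9.2.5.1). The distortion is therefore largest for all-cause AEs and smaller for related ones.
- **Maintenance is part of the regimen.** Section 6 counts rituximab as study drug, and the reasons for the amendment say the primary endpoint needs 25 months of follow-up. This stands. A reader might conclude that a Week 12 table should replace the full-period one, but that would redefine the primary endpoint and move late infections and second malignancies out of it.
- **The study is small and descriptive.** An observed 1/3 has an exact 95% interval of about 1% to 91%, so chance outweighs the shift shown above. That is true, but the unequal window is a systematic difference that can be removed cheaply, and descriptive tables still need comparable denominators.

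A later SAP could deal with AE windows, but the text does not say that it will.

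**Conclusion.** The concern holds within limits. As written, by-dose frequencies of background and late all-cause AEs, and of worst-grade laboratory values arising after Week 12, mix toxicity with disease control and maintenance exposure. The difference in windows, 12 against up to 108 weeks, comes straight from the schedule and needs no assumption beyond completed maintenance.

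The effect on incidence is illustrative. It rests on an assumed constant rate of 0.2 to 0.8 first events per patient-year, equal at both doses. A reader might take 25% against 56% in a cohort of 3 as the expected distortion. It is an extreme case: it needs one patient against three in maintenance, all completing it, and it does not describe the early cytopenias that dominate Betalutin's known toxicity. The direction is clear for late and background events; the size in this trial cannot be known in advance.

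**What to change.** In Section 10.1, keep the full-period AE table as the summary of the primary endpoint and add two displays by Betalutin dose:

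- **Day 0 to Week 12:** AE and worst-grade laboratory tables restricted to this period for every patient, named as the tables for comparing doses. State how the ±7-day window of the Week 12 visit is handled, and show how many patients were observed for the whole period.
- **After Week 12, including maintenance:** an AE table with patient-time at risk and events per patient-year.

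Onset dates are already recorded on the AE page (Section 9.2.4), so neither data collection nor patient management changes. The cost is wording in Section 10.1 or the SAP and the extra tables. With 3 to 6 patients per dose the late-period rates will be sparse, and should be shown with their event counts and patient-time so that no one over-reads them.
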